The time frame for data query will be from IRB approval (2020) until December 31, 2023. The electronic medical record (EMR) may be used in order to identify participants who match study defined demographic criteria.

Primary Outcome: Delayed complications found on repeat imaging

Secondary Outcomes: Timing to repeat imaging/ intervention, interventions performed based on complications found, mortality, length of stay, blood transfusion requirements, VTE prophylaxis, and 30 day readmission variables [readmission within 30 days for spleen and/or liver injury, readmission CT scan, interventions performed].

Variables

List specific variables to be collected & analyzed: Age, sex, time from injury, Injury Severity Score (ISS), Abbreviated Injury Scale (AIS), Trauma and Injury Severity Score (TRISS), mechanism of injury, initial vital signs, anticoagulant use and reversal agents, initial and repeat imaging, grade of organs injured, complications found, details regarding initial and any delayed interventions, blood transfusions, details regarding venous thromboembolism prophylaxis, venous thromboembolism complications, hospital length of stay, intensive care unit length of stay, mortality, and 30 day readmission variables [readmission within 30 days for spleen and/or liver injury, readmission CT scan, interventions performed].

Data Collection and Statistical Analysis

Standardized data will be collected for each patient meeting inclusion criteria (see data collection tool). The de-identified data for each patient will be entered into a secure REDCap database. A total of 5,000 patients (3,500 splenic injuries and 1,500

hepatic injuries) is recommended to identify a significant difference between the non clinical change and clinical change group. Complications found on repeat imaging will be assessed using univariate and multivariate analysis.

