Categorical variables will be compared using Fisher's exact test or Chi-squared test. Continuous variables will be assessed using Student's t-test. For multivariate analysis, a mixed effect multinomial logistic regression will be run with a binary outcome of whether the patient had a delayed complication. Another mixed effect multinomial logistic regression will be run with a binary outcome of whether the patient had an intervention performed. Additional analysis will be completed to determine if there is optimal timing for repeat imaging to identify complications. Data will be reported as adjusted odds ratios with 95% confidence intervals. Statistical significance will be defined by a p<0.05.

Sample Size and Power Estimates

A retrospective pilot study was completed with 235 patients with splenic injuries and 365 hepatic injuries. Of the patients with splenic injuries, 105 underwent repeat imaging, 46 had organ specific complications, and 16 had an intervention performed. Of the patients with hepatic injuries, 122 underwent repeat imaging, 30 had organ specific complications, and 12 had an intervention performed.

Spleen Power Analysis

Combined complication rate for patients who had repeat imaging: 46/105 = 0.44Standard protocol complication rate: 18/38 = 0.47Physician discretion complication rate: 28/67 = 0.42

Complication Rate:	Complication Rate:	Odds Ratio	Sample Size
Standard protocol	Physician discretion		(Total Population)
0.46	0.43	0.89	8,614
0.47	0.42	0.82	3,100
0.48	0.41	0.75	1,582

Liver Power Analysis

Combined complication rate for patients who had repeat imaging: 30/122 = 0.25Standard protocol complication rate: 10/50 = 0.20Physician discretion complication rate: 20/72 = 0.27

Complication Rate: Standard protocol	Complication Rate: Physician discretion	Odds Ratio	Sample Size (Total Population)
0.21	0.26	1.32	2,256
0.20	0.27	1.48	1,150
0.19	0.28	1.66	696

Consent Procedures

This is a retrospective observational study in which data will be retrospectively recorded on patients according to institutional protocols. Data will be input into REDcap database without any patient identifiers. Thus, a waiver of consent is requested.

Confidentiality and Privacy

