Hemobilia New area of hepatic injury not previously recognized on initial workup Hepatic infarct (not post intervention)
Abscess Fulminant liver failure
Bile leak/biloma
Unexpected thrombosis (of hepatic and related vessels) Need for OR/intervention other than initial Other:
Spleen Complications (defined as complications found during hospital admission, check all that apply): Increased bleeding/increased hemoperitoneum Pseudoaneurysm
Delayed rupture
New area of splenic injury not previously recognized on initial workup Splenic infarct (not post intervention) Abscess
Unexpected thrombosis (of splenic and related vessels)
Pancreatic fistula
Arteriovenous fistula Need for OR/intervention other than initial
Other:
Intervention Information
Initial Intervention (prior to repeat imaging, circle one): YES NO
Time from initial presentation in hours:
Type of intervention (check one): OR (damage control?) IR Other:
What was performed?
Post-Imaging Intervention (following repeat imaging, circle one): YES NO
Time from initial presentation in hours:
Type of intervention (check one):
OR
OR IR Other:
What was performed?

Intervention Information (continued)		
Was there a complication from an interv Migration of coil Rupture of vessel Pancreatic fistula post Abscess Need for repeat interv Other:	t-splenectomy rention/surgery	zation)? Check all that apply:
Transfusion Information Total refers t	o sum of product during admissio	n. Record in both units and volume (ml).
Transfusion during hospital admission?	(circle one): YES	NO
4h whole blood (units/ml):	4h pRBC (units/ml):	4h FFP (units/ml):
4h platelet (packs/ml):	24h whole blood (units/ml):	24h pRBC (units/ml):
24h FFP (units/ml):	24h platelet (packs/ml):	
Total whole blood (units/ml):	Total pRBC (units/ml):	
Total FFP (units/ml):	Total platelet (packs/ml):	_
VTE prophylaxis:		
Did patient receive VTE prophylaxis dur	ring admission? (Circle one):	YES NO
Timing of initiation of VTE propl	hylaxis from initial presentation in	hours:
Type of VTE prophylaxis (Chec Enoxaparin Subcutaneous Other:		
VTE documented? (Circle one):	YES NO	
Did the patient receive therapeutic antic	coagulation during their hospital ad	Imission? (Circle one): YES NO
Therapeutic Anticoagulation ag	ent:	
Outcome Data:		
Hospital LOS:		
ICU LOS:		
Mortality (Circle one): YES	NO	
Mortality timing from admission (in days	s):	

Outcome Data (continued):

Readmission within 30 days (Circle on	e):	YES		NO		
Readmission CT scan (Circle one):	YES		NO			

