First Repeat Imaging Hours from Admission	If yes checked for First Repeat Imaging, numerical value for when repeatimaging was performed in hours from admission.
Reason for First Repeat Imaging	If yes checked for First Repeat Imaging, single choice for best reason for scan. Options include:
	Clinical Change: Repeat imaging prompted by patient factors including, but not limited to, vital sign changes, lab abnormalities, abdominal pain, and patient symptoms.
	Non-Clinical Change: Repeat imaging prompted by institutional protocol/recommendations, individual physician practice pattern, or that performed on a scheduled basis.
First Repeat Imaging Findings	If yes checked for First Repeat Imaging, free text of organ specific (hepatic or splenic) imaging findings.
Organ Specific Delayed Complication	tions
Liver Complications	Liver specific complications found during hospital admission. Check all that apply. Options include:
	Increased bleeding, including increased hemoperitoneum. Pseudoaneurysm Hemobilia New area of hepatic injury not previously recognized on initial workup. Hepatic infarct (not post-IR/post-intervention). Abscess Fulminant liver failure Bile leak/biloma Unexpected thrombosis (of hepatic and related vessels) Need for OR/intervention other than initial Other (free text)

Organ Specific Delayed Complications (continued)

Spleen Complications	Spleen specific complications found during hospital admission. Check all that apply. Options include:
	Increased bleeding, including increased hemoperitoneum. Pseudoaneurysm Delayed rupture. New area of splenic injury not previously recognized on initial workup. Splenic infarct (not post-IR/post-intervention). Abscess Unexpected thrombosis (of splenic and related vessels) Pancreatic fistula Arteriovenous fistula Need for OR/intervention other than initial Other (free text)
Intervention Information	
Initial Intervention	Intervention for hepatic and/or splenic injury prior to repeat imaging (can occur post-initial imaging assessment). Yes/No dropdown menu. Yes = intervention performed for hepatic and/or splenic injury at initial assessment, prior to repeat imaging. No = no intervention performed for hepatic and/or splenic injury at initial assessment, prior to repeat imaging.
Initial Intervention Timing	If yes checked for Initial Intervention, numerical value for time to intervention from presentation (in hours).

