Readmission within 30 days	Yes/No dropdown menu for readmission within 30 days of hospital discharge. Readmission specifically for splenic or hepatic injury (not for concomitant injuries). Yes = patient readmitted within 30 days of initial discharge. No = patient not readmitted within 30 days of initial discharge.
Readmission CT scan	Yes/No dropdown menu for readmission CT scan. Yes = CT scan performed during readmission. No = No scan performed during readmission. If multiple scans were performed, select Yes.
Readmission CT scan findings	Free text entry for organ specific (splenic or hepatic) findings on readmission CT scan.
Intervention Performed on Readmission	Yes/No dropdown menu for intervention performed on readmission. Only include interventions performed for splenic or hepatic injury. Yes = intervention performed for splenic or hepatic injury on readmission. No = no intervention performed on readmission for splenic or hepatic injury.
Reason for Intervention on Readmission	Free text entry for reason for organ specific intervention upon readmission.
Type of Intervention on Readmission	Free text entry for type of intervention performed on readmission.

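### The primary outcome is complications found on repeat imaging, but the coded fields count any in-admission complication and the imaging reason covers only the first repeat scan, so events can be counted toward a scan that did not find them

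*Supplement*

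**What the plan says.** - **Outcome.** The protocol's Methods section states "Primary Outcome: Delayed complications found on repeat imaging".
- **Comparison.** Under Data Collection and Statistical Analysis, the total of 5,000 patients "is recommended to identify a significant difference between the non clinical change and clinical change group".
- **Model.** The same section plans a mixed-effect logistic regression "with a binary outcome of whether the patient had a delayed complication". It gives no rule on which scan found the complication, and none restricting the model to re-imaged patients.
- **Outcome fields.** In the data dictionary, under Organ Specific Delayed Complications, the spleen entry is "Spleen specific complications found during hospital admission. Check all that apply" and the liver entry is "Liver specific complications found during hospital admission. Check all that apply". The data collection tool defines them the same way. Both tick-lists include the need for an operation or intervention beyond the initial one, which is a treatment event and not an imaging finding.
- **Group field.** The dictionary entry on the reason for repeat imaging reads "If yes checked for First Repeat Imaging, single choice for best reason for scan". Type, hours, reason and free-text findings are collected for the first repeat scan. No block exists for a second or later scan.

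**The concern.** The outcome and the group label refer to different things. The label belongs to one scan, while the coded outcome belongs to the whole admission. Take a patient with a clean scheduled first scan, then a symptom-driven second scan that shows a pseudoaneurysm. In the coded data this patient is NCC with a complication, which reads as yield for a scan that did not show the lesion. The same happens when the lesion is recognised clinically or at operation.

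The complication fields also do not depend on repeat imaging having been done. A patient never re-imaged can have a ticked complication and so be an event in the patient-level regression, although nothing was found on repeat imaging.

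The stake is the contrast on which the study is sized. The planned differences are 5 points for spleen and 7 for liver, so a modest number of events not found by the index scan can dilute, inflate or nearly erase them.

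**Working it through.** **1. Reproduce the plan's figures.** The inputs are the rates in the Spleen and Liver Power Analysis tables: 0.47 (standard protocol, now NCC) v 0.42 (physician discretion, now CC) for spleen, and 0.20 v 0.27 for liver. The plan states a significance level of 0.05. It does not state power, sidedness or allocation. Two-sided 0.05, 80% power and 1:1 allocation reproduce all six rows of the two tables, using

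n per group = [1.96·√(2p̄(1−p̄)) + 0.8416·√(p₁(1−p₁) + p₂(1−p₂))]² / (p₁−p₂)²

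- Spleen: [1.96·√0.49395 + 0.8416·√0.4927]² / 0.05² gives 1,550 per group, 3,100 in total, as stated.
- Liver: [1.96·√0.35955 + 0.8416·√0.3571]² / 0.07² gives 575 per group, 1,150 in total, as stated.

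**2. Scenario A (assumed): both groups gain events.** Treat the planned rates as the true first-scan rates. Let a share f of patients negative on the first scan have a complication found later or by another route, and let the form count it. Each rate becomes p + (1−p)·f, so the difference shrinks by the factor (1−f). For spleen at f = 0.10, 0.47 + 0.53×0.10 = 0.523 and 0.42 + 0.58×0.10 = 0.478, a difference of 0.045.

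| f | Spleen rates (NCC v CC) | Power at 3,100 | N for 80% | Liver rates (NCC v CC) | Power at 1,150 | N for 80% |
|---|---|---|---|---|---|---|
| 0 | 0.470 v 0.420 | 80% | 3,100 | 0.200 v 0.270 | 80% | 1,150 |
| 5% | 0.4965 v 0.449 | 75.5% | 3,468 | 0.240 v 0.3065 | 71.6% | 1,408 |
| 10% | 0.523 v 0.478 | 70.7% | 3,874 | 0.280 v 0.343 | 63.6% | 1,696 |
| 20% | 0.576 v 0.536 | 61.1% | 4,842 | 0.360 v 0.416 | 49.5% | 2,376 |

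The two N values are taken from the tables as patients who carry a group label. Whether planned enrolment yields that many re-imaged patients is a separate question.

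**3. Scenario B (assumed): only NCC gains events.**

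- Plus 2 points: spleen 0.49 v 0.42, difference 7 points. Liver 0.22 v 0.27, difference 5 points, power at 1,150 about 50%.
- Plus 5 points: spleen 0.52 v 0.42, difference 10 points. Liver 0.25 v 0.27, difference 2 points, power at 1,150 about 12%.

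The same error widens one organ's contrast and narrows the other's.

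**4. What 5 points means in patients.** At pilot rates, 3,500 × 105/235 = 1,564 splenic patients are re-imaged and 1,564 × 38/105 = 566 of them are NCC. Five per cent of 566 is about 28 patients. About 300 of the 566 (566 × 0.53) would be negative on the first scan, so 28 is roughly 9% of those.

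**The case against.** Much can be said for the plan, and several stronger readings should be resisted.

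- **Events are misassigned.** A reader might infer this as a fact. The documents support only that they can be. A complication seen on the first repeat scan is grouped correctly, and no frequency is given for the other routes.
- **The bias flatters routine imaging.** This is not shown. CC-first patients can also gain later events, and a clinically recognised complication may itself prompt a CC scan.
- **Misattribution could create the whole spleen difference.** The 28 patients above would equal it, but only if NCC gains all the extra events and CC none. No document gives such a figure.
- **Patients never re-imaged distort NCC v CC.** They have no reason for imaging and so no group. The pilot rates also used only re-imaged patients as denominator. The problem is confined to the regression, whose population is not stated.
- **Timing cannot be analysed.** Hours to the first repeat scan and to post-imaging intervention are collected, so yield by scan time can be studied for first-scan findings. What is missing is the discovery time of the complication itself.
- **Leaving out readmission CT findings is an error.** Readmission is its own aim and secondary outcome, with a "Free text entry for organ specific (splenic or hepatic) findings on readmission CT scan". Keeping it separate is a design choice.

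The best mitigation is the free-text field for first-scan findings. It would expose a clean first scan with a box ticked later. But it is uncoded, the analysis plan does not use it, and it cannot give the reason or time of a later scan. The core mismatch stands.

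**Conclusion.** The concern holds as a mismatch between the stated primary outcome and the coded data. As specified, the tick-boxes cannot separate complications found on the first repeat scan from those found on a later scan, clinically or at operation, and the analysis text gives no rule that would do so.

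The size is conditional. Steps 2 and 3 rest on assumed frequencies, on the planned rates being true first-scan rates, and on the inferred 80% power with 1:1 allocation. They show that a shift of a few points matters against differences of 5 and 7 points. They do not show that such a shift will occur, or in which direction.

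**What to change.** 1. For each ticked complication, add one coded field for how it was found (first repeat scan; later scan; clinically or at operation without a scan; before the repeat scan) and one for hours from presentation.
2. Define the primary NCC v CC outcome as a complication found on the first repeat scan, grouped by that scan's reason, among patients who had a first repeat scan. State that the regression for this contrast uses the same population.
3. Report in-admission complications from any source as a sensitivity analysis. Readmission CT findings may stay a separate secondary outcome.
4. Do not regroup patients by the reason of the scan that found the complication. Group would then depend on outcome, and later scans in complication-free patients are not recorded, so there would be no denominator.

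**Cost.** At pilot rates the two fields are needed in about 3,500 × 46/235 = 685 splenic and 1,500 × 30/365 = 123 hepatic charts, with no new procedures. The narrower definition gives somewhat fewer primary events. For charts already abstracted, the first-scan free text can identify some answers, but events found on later scans need a return to the record.
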